- 5. Participants who receive anti-PD-1 therapy as adjuvant treatment following complete resection of liver cancer and have disease recurrence (unresectable locoregional disease or distant metastases) are eligible if they progressed while on active treatment or within 6 months of stopping anti-PD-1 therapy. This will be considered the first line of systemic therapy.

For these participants, the following applies:

- 1) a second assessment to confirm disease progression beyond recurrence is not required; and
- 2) they must have received at least 2 prior doses of anti-PD-1/PD-L1 mAb.
- 6. Barcelona Clinic Liver Cancer (BCLC) stage B or C (see Appendix 8, Section 10.8).
- 7. Liver function status should be Child-Pugh (CP) Class A (see Appendix 9, Section 10.9) within 7 days prior to the first dose of study intervention. CP status should be calculated based on clinical findings and laboratory results during the screening period.
- 8. Eastern Cooperative Oncology Group (ECOG) Performance Status (PS) of 0 or 1 within 7 days prior to prior to the first dose of study intervention.
- 9. At least one measurable lesion by CT scan or MRI according to RECIST 1.1. Tumor lesions situated in a previously irradiated area, or in an area subjected to other loco-regional therapy, may be considered measurable if there has been demonstrated progression in the lesion.
- 10. Have adequate organ function as defined in the following table (Table 5–1). Specimens must be collected within 7 days prior to the start of study intervention.

Table 5-1: Adequate Organ Function Laboratory Values

System	Laboratory Value
Hematological	
Absolute neutrophil count (ANC)	≥1000/mm³
Platelets	≥60 000/mm³
Hemoglobin	≥8.5 g/dL ^a
Renal	
Creatinine OR Measured or calculated ^b creatinine clearance (GFR can also be used in place of creatinine or CrCl)	≤1.5 × ULN OR ≥30 mL/min for participant with creatinine levels >1.5 × institutional ULN
Hepatic/Pancreatic	
Total bilirubin	≤2 mg/dL. Mildly elevated total bilirubin (<6 mg/dL) is allowed if Gilbert's syndrome is documented.
AST and ALT	≤5.0 × ULN
Lipase	≤ 3 x ULN without symptoms
Coagulation	
International normalized ratio (INR) OR prothrombin time (PT) Activated partial thromboplastin time (aPTT)	PT-INR <2.3 and aPTT <1.5 x ULN unless receiving treatment with therapeutic anticoagulation

Page 44 of 141

Table 5-1: Adequate Organ Function Laboratory Values

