- The start of new anti-cancer treatment
- Withdrawal of consent
- Death
- The end of the study

Response assessment:

RECIST 1.1 (see Appendix 5, Section 10.5.1) and mRECIST criteria for HCC (see Appendix 5, Section 10.5.2) will be used for radiological tumor evaluation in this study. iRECIST (see Appendix 5, Section 10.5.3, Table 10–11 and Figure 10–1) can be used by the investigator to assess tumor response and progression and support treatment-related decisions in this study.

By inclusion criteria, participants must have at least one evaluable and measurable lesion per RECIST 1.1 on the baseline scan. Tumor measurements and assessments are to be performed at the local sites and are to be entered in the eCRF. All scans should be interpreted by the same radiologist/investigator during the study, where at all possible. Any lesion that has been previously treated with radiotherapy should be considered as a non-target lesion. However, if a lesion previously treated with radiotherapy has clearly progressed on the baseline/screening scan, it can be considered as a measurable lesion.

The minimum time interval required between two tumor assessments for determination of SD is 6 weeks. Objective response should be confirmed by a repeat imaging assessment. CT/MRI scans for confirmation of response should be performed no sooner than 4 weeks after the initial scan demonstrating PR or CR. Participants will then return to regular scheduled imaging, starting with the next scheduled imaging time point. Participants who receive additional imaging for confirmation do not need to undergo the next scheduled tumor imaging if it is less than 4 weeks later. For these participants, tumor imaging may resume at the subsequent scheduled imaging time point.

Imaging data:

All image files (coded with study participant number and in Digital Imaging and Communications in Medicine (DICOM) format for CT/MRIs and bone scans) as well as imaging-related adjunctive data (e.g. dose of contrast agent) must be stored locally. In this study, image files and imaging-related adjunctive data will also be collected centrally by an imaging core laboratory designated by Bayer starting at the beginning of the study for a centralized independent imaging review of tumor response9. Further guidance on the acquisition of CT/MRIs and bone scans as well as information on how to transmit image files to the imaging core laboratory will be provided in the Imaging Guidance for this study.

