10.5 Appendix 5: Tumor response criteria (RECIST 1.1, mRECIST for HCC, and iRECIST)

Response and progression will be evaluated in this study using RECIST 1.1 (Section 10.5.1). Modified RECIST for HCC (Section 10.5.2) and iRECIST (Section 10.5.3) will be used as exploratory analyses.

10.5.1 **RECIST 1.1**

The RECIST 1.1 criteria, based on the measurement of the longest diameter of tumor lesions, were designed and validated to assess treatment response in solid tumors (Eisenhauer et al. 2009).

Measurable Disease:

Non-nodal tumor lesions: Measurable lesions are defined as those that can be accurately measured in at least one dimension (longest diameter to be recorded) with a minimum size of:

- 10 mm by CT scan (CT scan slice thickness no greater than 5 mm) or MRI. If scans with slice thicknesses greater than 5mm are used, the minimum size should be twice the slice thickness.
- 20 mm by chest X-ray
- 10 mm caliper measurement by clinical examination (lesions which cannot be accurately measured with calipers should be recorded as non-measurable)

Malignant lymph nodes: To be considered pathologically enlarged and measurable, a lymph node must be ≥ 15 mm in short axis when assessed by CT scan (CT scan slice thickness recommended to be no greater than 5 mm). At baseline and in follow-up, only the short axis will be measured and followed.

Lytic bone lesions or mixed lytic-blastic lesions, with identifiable soft tissue components that can be evaluated by CT or MRI, can be considered as measurable lesions if the soft tissue component meets the definition of measurability.

Tumor lesions situated in a previously irradiated area are not considered measurable unless there has been demonstrated progression in the lesion.

Baseline assessment

Page 114 of 141

Non-Measurable Disease: All other lesions (or sites of disease), including small lesions (longest diameter <10 mm or pathological lymph nodes with ≥10 to < 15mm short axis) are considered non-measurable disease. Leptomeningeal disease, ascites, pleural/pericardial effusions, lymphangitic involvement of skin or lung, inflammatory breast disease, abdominal masses/ abdominal organomegaly identified by physical examination that is not measurable by reproducible imaging techniques and blastic bone lesions are all non-measurable.

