Target Lesions: All measurable lesions up to a maximum of 2 lesions per organ and 5 lesions in total, representative of all involved organs should be identified as *target lesions* and be recorded and measured at baseline. These 5 lesions should be selected on the basis of their size (lesion with the longest diameter), be representative of all involved organs and should be suitable for reproducible repeated measurements. A sum of the diameters (longest for non-nodal lesions, short axis for nodal lesions) for *all target lesions* will be calculated and reported as the baseline sum diameters. If lymph nodes are to be included in the sum, then as noted above, only the short axis is added into the sum. The baseline sum diameters will be used as reference to further characterize any objective tumor regression of the measurable dimension of the disease. If there are >5 measurable lesions, those not selected as *target lesions* will be considered together with non-measurable disease as *non-target lesions*.

Non-target Lesions: All non-measurable lesions (or sites of disease) plus any measurable lesions over and above the 5 listed as *target lesions*, including pathological lymph nodes (with short axis ≥10 mm and < 15 mm) should be identified as non-target lesions and should also be recorded at baseline. Measurements are not required but these lesions should be noted at baseline and should be followed as "present", "absent" or in rare cases "unequivocal progression". In addition, it is possible to record multiple non-target lesions involving the same organ as a single item on the eCRF (e.g.; 'multiple enlarged pelvic lymph nodes' or 'multiple liver metastases').

Best Response

The best overall response is the best response recorded from the start of the study intervention until the end of intervention. The participant's best overall response assignment will depend on the findings of both target and non-target disease and will also take into consideration the appearance of new lesions. While some non-target lesions may actually be measurable, they need not be measured and instead should be assessed only qualitatively at the time points specified in the protocol.

All participants will have their best response on study classified as outlined below:

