Complete Response (CR): Disappearance of all clinical and radiological evidence of tumor (both *target* and *non-target*). Any pathological lymph nodes (whether target or non-target) must have a reduction in short axis to < 10mm.

Partial Response (PR): At least a 30% decrease in the sum of diameters of target lesions taking as reference the baseline sum, no unequivocal progression of existing non-target lesions and no appearance of new lesions.

Stable Disease (SD): Steady state of disease. Neither sufficient shrinkage to qualify for PR nor sufficient increase to qualify for PD, no unequivocal progression of existing non-target lesions and no appearance of new lesions.

Progressive Disease (PD): At least a 20% increase in the sum of diameters of target lesions taking as reference the smallest sum on study (this includes the baseline sum if that is the smallest on study). In addition to the relative increase of 20%, the sum must also demonstrate

Page 115 of 141

an absolute increase of at least 5mm. Unequivocal progression of existing non-target lesions or the appearance of one or more new lesions will also constitute progressive disease. (Note: the appearance of one or more new lesions is also considered progression). Ascites or pleural effusion will be recorded as disease progression only if proven malignant.

Lymph nodes identified as target lesions should always have the actual short axis measurement recorded (measured in the same anatomical plane as the baseline examination), even if the nodes regress to below 10 mm on study. This means that when lymph nodes are included as target lesions, the 'sum' of lesions may not be zero even if complete response criteria are met, since a normal lymph node is defined as having a short axis of <10mm.

To achieve unequivocal progression in participants with measurable disease on the basis of the non-target disease, there must be an overall level of substantial worsening in non-target disease such that, even in presence of SD or PR in target disease, the overall tumor burden has increased sufficiently to merit withdrawal of study intervention. A modest 'increase' in the size of one or more non-target lesions is usually not sufficient to qualify for unequivocal.

In the absence of measurable disease, the same general concepts apply here as noted above.

Response duration

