Results from a number of previous clinical studies in HCC have demonstrated that RECIST does not adequately capture the extent of tumor necrosis induced by interventional therapies or new molecular targeting drugs. Only viable tumor, assessed by properly designed CT or MRI studies, should be included in the tumor burden, and viable tumor should be defined as uptake of contrast agent in the arterial phase of dynamic imaging studies. Consequently, a modification of RECIST was first proposed by a panel of experts, and further expanded. This proposal is based on the fact that the diameter of the target lesions with viable tumor tissue should be the basis of measurements for intrahepatic lesions. The measurement of the longest viable tumor diameter for the assessment of response according to mRECIST can be only applied in case of typical lesions. Conversely, for non-enhancing atypical lesions, as well as for any extrahepatic neoplastic niches, the measurements of the longest overall tumor diameter as per conventional RECIST should prevail. In addition, there are specific modifications of the original criteria regarding the assessment of vascular invasion, lymph nodes, ascites, pleural effusion, and new lesions (European Association for the Study of the Liver [EASL]- European Organisation for Research and Treatment of Cancer [EORTC] clinical practice guidelines) (EASL-EORTC 2012).

The expert panel has adopted the concept of viable tumor endorsed by EASL and proposed amendments to RECIST in the determination of tumor response for HCC, which have been incorporated into the criteria in this trial as described herein.

Definitions

Intrahepatic lesions: Malignant findings within the liver parenchyma, the portal vein, and the porta hepatis region. The rules for the assessment of intrahepatic lesions (including when a new lesion is considered to have appeared) incorporate the referenced modifications for HCC.

Page 118 of 141

Extrahepatic lesions: All malignant lesions, other than those defined as intrahepatic as above. These lesions will be assessed using the standard RECIST 1.1 approach.

Measurable lesions: Lesions that, at baseline, meet the requirements for being reproducibly quantifiable. The requirements are different for intrahepatic and extrahepatic lesions, and are described below. Lesions that meet the requirements are considered eligible for quantitative assessment during the study.

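### Criterion 9 requires demonstrated progression before any loco-regionally treated lesion counts as measurable; the RECIST 1.1 rules behind the primary ORR require it only for irradiated lesions

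*Protocol*

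**What the plan says.** Four places in the protocol say when a previously treated lesion counts as measurable.

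- **Section 5.1, criterion 9 (eligibility).** Lesions in an irradiated area "or in an area subjected to other loco-regional therapy, may be considered measurable if there has been demonstrated progression in the lesion". The condition covers radiotherapy and other loco-regional therapy.
- **Section 8.1, Response assessment.** "Any lesion that has been previously treated with radiotherapy should be considered as a non-target lesion". The exception reads: "if a lesion previously treated with radiotherapy has clearly progressed on the baseline/screening scan, it can be considered as a measurable lesion". Only radiotherapy is named.
- **Section 10.5.1, RECIST 1.1.** "Tumor lesions situated in a previously irradiated area are not considered measurable unless there has been demonstrated progression in the lesion". Only irradiation is named.
- **Section 10.5.2, mRECIST for HCC.** The same sentence as in 10.5.1.

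Section 10.5.1 then builds the target set from "All measurable lesions up to a maximum of 2 lesions per organ and 5 lesions in total, representative of all involved organs". On choice among them it says: "These 5 lesions should be selected on the basis of their size (lesion with the longest diameter"; the same sentence adds that targets should represent the involved organs and suit reproducible repeated measurement. Partial response is "At least a 30% decrease in the sum of diameters of target lesions taking as reference the baseline sum".

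The primary endpoint is ORR by RECIST 1.1 on central review (protocol 9.4.1.2; SAP v3.0, 5.3.1). SAP v3.0 gives no lesion-level rule and plans no sensitivity analysis for it (5.3.3).

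**The concern.** The rule that admits a participant and the rule that measures the response are not the same. A participant can enter on one small active lesion while also carrying a larger liver lesion that was treated earlier and has not progressed. Criterion 9 would not accept that second lesion as measurable. Section 10.5.1 as written does, provided it is at least 10 mm and can be accurately measured.

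The protocol recognises the underlying weakness. In introducing mRECIST it says that "RECIST does not adequately capture the extent of tumor necrosis induced by interventional therapies". RECIST 1.1 takes the whole diameter, so a dead lesion stays in the sum. It can hide real shrinkage of active disease and turn a response into stable disease. What is at stake is the classification of individual participants on the primary endpoint, against a pilot criterion of 8 responders in 26 and final criteria of 27 in 93 or 34 in 119.

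**Working it through.** **1. The plan's own figures (protocol 9.1 and 9.2).** Inputs: null 20%, target 35%, one-sided alpha 0.025, pilot rule at least 8/26, 67 further participants. Exact binomial tails at 20%:

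- at least 27/93: 0.0238 (26/93 would give 0.0408)
- at least 34/119: 0.0158 (33/119 would give 0.0264)

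Conditional power at 35% is the sum, over pilot counts of 8 or more, of the pilot probability times the chance of enough responders among the 67, divided by the chance of passing the pilot. In scenario 2 both cohorts must pass. It is 95.5% in scenario 1 and 99.0% in scenario 2, so the stated minimum of 95% reproduces. The chance that one cohort reaches 8/26 at 35% is 74.0%. The fix changes none of these figures.

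**2. Effect of an unchanged target.** Let T be the baseline diameter of the unchanged treated lesion, A the baseline sum of the other targets, and s = T/(T + A). If the other targets shrink by a fraction x, partial response needs xA >= 0.30(T + A), so x >= 0.30/(1 - s).

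| s | Shrinkage needed in the other targets |
|---|---|
| 0 | 30% |
| 25% | 40% |
| 50% | 60% |
| 70% | 100% |
| above 70% | not reachable |

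**3. Lesion pairs (assumed sizes).**

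| Treated, unchanged | Active | s | Decrease needed (0.30 x sum) | As share of active lesion |
|---|---|---|---|---|
| 30 mm | 30 mm | 50% | 18 mm | 60% |
| 40 mm | 20 mm | 66.7% | 18 mm | 90% |
| 60 mm | 25 mm | 70.6% | 25.5 mm | 102%, impossible |

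In the last pair, complete disappearance of the active lesion gives 25/85 = 29.4%, which is stable disease.

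**4. The same participant under criterion 9's rule.** The 60 mm lesion becomes non-target. The target response is then complete, and the non-target response is neither complete nor progressive. With no new lesion, Table 10-5 scores this as partial response. The wording alone changes the result.

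**5. Sensitivity of the design to lost responses (assumption).** The documents give no rate. Suppose a fraction f of true responses at 35% is lost in this way, with f from 0 to 20%, so that the observed rate is 0.35(1 - f).

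| f | Observed ORR | One cohort reaches 8/26 | Conditional power, scenario 1 | Scenario 2 |
|---|---|---|---|---|
| 0 | 35% | 74.0% | 95.5% | 99.0% |
| 5% | 33.25% | 67.6% | 91.5% | 97.6% |
| 10% | 31.5% | 60.5% | 85.3% | 94.9% |
| 20% | 28.0% | 44.9% | 64.9% | 82.5% |

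This shows how much a few misclassified responses would matter. It does not estimate how many there are.

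**The case against.** **Silence rather than conflict.** No passage states that a non-progressing, loco-regionally treated lesion is measurable. Section 8.1 refers back to the inclusion criteria for measurable disease, so a careful reader could carry criterion 9's rule throughout. That is a sensible reading, but not a secure one. Sections 8.1 and 10.5.1 each restate the condition and each time leave out the second half, and 10.5.1 is the text cited for response criteria.

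**Not a mandatory target.** From the size rule a reader might infer that the larger treated lesion has to be a target. The documents do not go that far. The lesion must be accurately measurable, and organ representation and reproducibility also count, so a reader of the scans has room to pass over it. It can be chosen; it need not be.

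**Direction.** A reader might infer a proven downward bias in ORR. That follows only where the treated lesion does not change. One still shrinking after the earlier procedure would add to the decrease and could push ORR up.

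**mRECIST.** Section 10.5.2 has the same gap but less exposure. Only the enhancing part of a typical liver lesion is measured, and typical lesions are preferred as targets. Its ORR is exploratory and investigator-assessed, so it cannot affect the primary endpoint.

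**Central against site reading.** Divergence between the two is possible, but the documents do not show it. The Imaging Guidance named in Section 8.1 was not available and may already settle the rule.

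**Practical reach.** SAP v3.0 records that recruitment stopped early and lists interim analyses as not applicable, so the 93 or 119 participant test may not be run as designed. This stands, but central ORR remains the primary endpoint.

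**Conclusion.** The inconsistency is real and should be corrected. Criterion 9 covers all loco-regional therapy, while Sections 8.1, 10.5.1 and 10.5.2 cover radiotherapy only. Under 10.5.1 as written, a non-progressing treated liver lesion can enter the target sum and change a participant's result on the primary endpoint.

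The size is exact for an individual, 0.30/(1 - s), assuming that the lesion does not change. It is unknown for the trial. Loco-regional therapy is recorded as history in Table 1-1, but nothing states how many participants have a treated, non-progressing lesion large enough to be a target. The supportable conclusion is that the primary ORR can be distorted for reasons unrelated to study treatment, with downward the likely direction for inert lesions and the net direction undetermined. The conclusion also assumes that the Imaging Guidance and SAP v2.0, which were not available, do not already impose a single rule.

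**What to change.** Use one measurability rule throughout.

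1. In Sections 10.5.1 and 8.1, which govern the primary endpoint, extend the sentence from irradiated lesions to lesions in an area given other loco-regional therapy, as criterion 9 does. Such lesions are non-target unless progression in the lesion has been demonstrated.
2. Reconcile the two progression tests. Section 8.1 asks for clear progression on the baseline or screening scan, whereas criterion 9 asks for demonstrated progression without naming a scan. Adopting criterion 9's test in 8.1 leaves eligibility untouched.
3. Make the same edit in Section 10.5.2, for consistency only.
4. Give the central readers the same rule, with the loco-regional treatment history already collected at baseline.

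The cost is one phrase in three places, the reconciled test in 8.1, and a line in the imaging guidance. Some participants will have fewer target lesions. None loses eligibility, because criterion 9 already applies the rule at entry.
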